10.6 Sensitivity Analysis for the Efficacy Endpoint of SVR₁₂

In addition to presenting the secondary efficacy endpoint of SVR₁₂ as described in Section 10.4, two sensitivity analyses of SVR₁₂ will be presented using the following modified populations. The first sensitivity analysis of SVR₁₂ will be conducted using a Modified Intention-to-Treat Genotype (mITT-I-GT) population that includes subjects who receive at least 1 dose of study drug in Study M14-423 (with imputation as described in Section 6.3) but excludes the subjects who are not of HCV genotype 1 infection. The mITT-I-GT population is used to reduce the risk of bias that could occur due to enrolled population deviating from the protocol selected study population.

The other sensitivity analysis of SVR₁₂ will be conducted using a Modified Intention-to-Treat Genotype and Virologic Failure (mITT-I-GT+VF) population. The mITT-I-GT+VF population is used to reduce the risk of bias that could occur due to either discordant HCV genotype or irrelevant failures unrelated to study drug. The mITT-I-GT+VF population includes all subjects who receive at least 1 dose of study drug in Study M14-423 (with imputation as described in Section 6.3) but excludes the subjects who are not of HCV genotype 1 infection and the subjects who did not achieve SVR₁₂ due to reasons other than on treatment virologic failure or relapse.

10.7 Additional Efficacy Analyses

The following additional HCV RNA efficacy endpoints will be summarized and analyzed on the ITT-I population, as specified:

- The number and percentage of subjects with on-treatment virologic failure;
- The number and percentage of subjects with post-treatment relapse;
- The number and percentage of subjects with documented re-infection;
- The number and percentage of subjects with RVR;
- The number and percentage of subject with EOTR;
- The number and percentage with unquantifiable HCV RNA at each post-baseline visit throughout the Treatment Period (using data from the central laboratory as observed, i.e., no imputation for missing data);
- The number and percentage of subjects with HCV RNA < LLOQ 24 weeks after the last actual dose of study drug (SVR₂₄);
- Reasons for not achieving SVR₂₄ for subjects who do not;
- Mean change from baseline in prothrombin time (PT), International normalized ratio (INR), FibroTest, and albumin to each applicable post-baseline time point;
- The number of subjects who fail to suppress and accompanying listing;
- The number of subjects who breakthrough any time during treatment and accompanying listing;
- The number of completers with final on-treatment HCV RNA < LLOQ who relapse within the SVR₄ window, SVR₁₂ window, or SVR₂₄ window and accompanying listing;
- The concordance between SVR₁₂ and SVR₂₄ will be assessed.

In the above analyses that use the number and percentage of responders, 2-sided 95% Wilson score confidence interval for a binomial proportion will be calculated.

Imputations for missing data will be performed as described in Section 6.3 for analyses of SVR, RVR, and EOTR, where a missing response will be imputed as a failure after performing the described imputation. All other endpoints will be presented using data as observed. For the change from baseline to each post-baseline time point in PT/INR, Fibrotest, and albumin, descriptive statistics will be calculated.

The number and percent of subjects who fail to suppress HCV RNA and received at least 6 weeks of treatment (active study drug duration ≥ 36 days) will be tabulated along with the subject numbers corresponding to the subjects who failed to suppress.

The number of subjects who breakthrough at any time during treatment and within each protocol-specified visit (defined in Table 2) will be summarized along with a corresponding listing displaying the subject numbers at the first occurrence of breakthrough.

The number of documented re-infected subjects who re-infected within the SVR₄ window, within the SVR₁₂ window, within the SVR₂₄ window (defined in Table 3), after the SVR₂₄ window and anytime post-treatment (study drug end day ≥ 3) will be summarized along with a corresponding listing of the subjects numbers displaying the window of the first occurrence/detection of re-infection.

The number of completers (defined as study drug duration ≥ 77 days for subjects assigned to 12 weeks of treatment and ≥ 154 days for subjects assigned to 24 weeks of treatment) with final on treatment HCV RNA $< \text{LLOQ}$ who relapse within the SVR₄ window, within the SVR₁₂ window, within the SVR₂₄ window (defined in Table 3), after the SVR₂₄ window and anytime post-treatment (study drug end day ≥ 3) will be summarized along with a corresponding listing displaying the first occurrence of relapse. A similar table and listing will be provided of Preterm Relapses for subjects who do not complete treatment (defined as study drug duration < 77 days for subjects assigned to 12 weeks of treatment and < 154 days for subjects assigned to 24 weeks of treatment) with HCV RNA $< \text{LLOQ}$ at the Final Treatment visit.

The concordance between SVR₁₂ and SVR₂₄ will be assessed by agreement between SVR₁₂ and SVR₂₄ and by the positive predictive value (PPV) and the negative predictive value (NPV) of SVR₁₂ on SVR₂₄. The agreement between SVR₁₂ and SVR₂₄ is defined as the number of subjects achieving both SVR₁₂ and SVR₂₄ and the number of subjects not achieving both SVR₁₂ and SVR₂₄ out of all subjects in the ITT population. The PPV of SVR₁₂ on SVR₂₄ is the proportion of subjects who achieve SVR₂₄ out of all subjects who

achieved SVR₁₂. The NPV of SVR₁₂ on SVR₂₄ is the proportion of subjects who do not achieve SVR₂₄ out of all subjects who do not achieve SVR₁₂.

10.8 Resistance Analyses

If possible, subjects treated with study drug who experience virologic failure will have resistance testing conducted if 1) they have on-treatment breakthrough; 2) if they have post-treatment relapse, with a study drug duration ≥ 77 days for subjects assigned to 12 weeks of treatment or with a study drug duration ≥ 154 days for subjects assigned to 24 weeks of treatment; or 3) if they have at least 6 weeks of treatment and fail to suppress by Week 6 (i.e., meet virologic stopping criteria). Subjects meeting one of these criteria will be referred to as subjects in the primary virologic failure (PVF) population, and a listing by subject that includes HCV subtype, IL28B genotype, reason for non-response, time point(s) sequenced as closest to time of VF, and HCV RNA value at the VF time point(s) will be produced for these subjects. In addition, all listings described below will display HCV subtype and reason for non-response in the subject identifier for each subject. A separate listing will delineate all subjects in the PVF population for whom no sequencing was performed (e.g., lost to follow-up while HCV RNA ≤ 1000 IU/mL).

Only samples with an HCV RNA level of ≥ 1000 IU/mL will undergo sequence analysis in order to allow accurate assessment of products of amplification. Therefore if the HCV RNA level at the time of virologic failure (VF) is < 1000 IU/mL, the sample closest in time after the failure with an HCV RNA level ≥ 1000 IU/mL will be used if available.

The regions of interest for next generation sequencing (NGS) from all evaluated time points in this study are those encoding full length NS3/4A, NS5A, and NS5B. The prototypic reference sequences used for analysis will be H77 for genotype 1a or Con1 for genotype 1b.

For each DAA target, resistance-associated amino acid variants will be identified by AbbVie Clinical Virology. Amino acid positions where resistance associated variants have been identified in vitro and/or in vivo are 1) for ABT-450: 36, 43, 55, 56, 80, 155,

156, and 168 in NS3 for genotype 1a; 56, 155, 156, and 168 in NS3 for genotype 1b; 2) for ABT-267: 28, 30, 31, 32, 58, and 93 in NS5A for genotype 1a; 28, 29, 30, 31, 32, 58, and 93 in NS5A for genotype 1b; and 3) for ABT-333: 316, 414, 446, 448, 451, 553, 554, 555, 556, 558, 559, and 561 in NS5B for genotype 1a; 316, 368, 411, 414, 445, 448, 553, 556, 558, and 559 in NS5B for genotype 1b. The final list of amino acid positions where resistance-associated variants have been identified will be included in the CSR.

The following definitions will be used in the resistance analyses:

- Baseline variant: a variant by NGS in a baseline sample ($\geq 2\%$ or $\geq 15\%$ prevalence within a subject's viral population depending on variant frequency threshold utilized) that was not present in the appropriate prototypic reference amino acid sequence for a given DAA target (NS3, NS5A, or NS5B).
- Post-baseline variant by NGS: an amino acid variant in a post baseline time point sample that was not detected at baseline ($< 2\%$) in the subject and is detectable in $\geq 2\%$ of the sequences from the post-baseline sample.
- Enriched variant: variant present in both the baseline and a post-baseline sample whose prevalence in the post-baseline sample is at least 20 percentage points greater than the prevalence in the baseline sample [(post-baseline % – baseline %) ≥ 20].
- Treatment-emergent variant: A post-baseline variant or an enriched variant.

The following will be provided for subjects who are in the PVF population and have resistance data available.

Listings by subject of all baseline variants ($\geq 2\%$ and $> 15\%$ detection thresholds) relative to prototypic reference sequence at signature resistance-associated amino acid positions will be provided for each DAA target (NS3, NS5A, and NS5B).

A listing by subject of all baseline variants ($\geq 15\%$ detection threshold) at non-signature amino acid positions will be provided for each DAA target (NS3/4A, NS5A and NS5B).

A listing by subject and time point of all treatment-emergent variants relative to the baseline amino acid sequences will be provided across all DAA targets (NS3, NS5A, and NS5B).

The number and percentage of subjects with post-baseline variants at signature amino acid positions or emerged variants at non-signature amino acid positions by, listed by amino acid position and variant within a DAA target at the time of VF compared to baseline will be summarized, along with the number of subjects within a DAA target and overall. The analyses will be grouped by HCV subtype (1a or 1b) and DAA target (NS3, NS5A, or NS5B) and will list the subject numbers of subjects with each variant. The number of subjects with resistance variants in 3 targets, 2 targets or 1 target will be provided.

Listings by subject and time point of all post-baseline variants relative to the baseline amino acid sequence will be provided for each DAA target (NS3, NS5A, and NS5B). In addition, a listing by subject and time point of all post-baseline variants at signature resistance-associated amino acid positions relative to the appropriate prototypic reference amino acid sequences will be provided.

For all subjects who experience VF, the persistence of resistance-associated variants for each target (NS3, NS5A, and NS5B) will be assessed by NGS at Post-Treatment Weeks 24 and 52 and at time points up to Post-Treatment Week 260 (5 years). The number and percentage of subjects with post-baseline variants at signature amino acid positions, listed by amino acid position and variant within a DAA target at each Post-Treatment time point compared to baseline will be summarized, along with the number of subjects within a DAA target and overall. Additionally, the number and percentage of subjects in whom a signature variant persisted at Post-Treatment Week 24 and 52 and time points up to Post-Treatment Week 260 (5 years) out of the total number of subjects with that emerged variant at the VF time point and at that time point will be summarized by DAA target, and variant. The number and percentage of subjects who still have a variant at a given Post-Treatment time point will be calculated out of all subjects with that variant at VF who have sequencing at that time point. The imputation described below will be used for PT Week 52 or time points up to Post-Treatment Week 260 (5 years). If a

signature variant is not detectable at Post-Treatment Week 24, the variant is imputed as not detectable at the Post-Treatment Week 52 and time points thereafter even if a sample from Post-Treatment Week 52 or later is not sequenced. If a signature variant is detectable at Post-Treatment Week 52 or later, then the variant is imputed as being detectable at earlier time points even if the sample at the earlier time point is not sequenced.

If resistance-associated variants are not detected by NGS in a given target for a subject either at the time of failure or in a post treatment sample, then that target will not be sequenced in subsequent samples from that subject.

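### In SAP 10.8 the signature-position counts at virologic failure and at each post-treatment time point use 'post-baseline' variants, so they omit the enriched variants that the SAP's own 'treatment-emergent' category includes

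*SAP*

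**What the plan says.** SAP 10.8 defines three terms for next generation sequencing (NGS).

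- *Post-baseline variant*: "an amino acid variant in a post baseline time point sample that was not detected at baseline", with non-detection set at below 2% and detection later at 2% or more.
- *Enriched*, by contrast, means a "variant present in both the baseline and a post-baseline sample whose prevalence in the post-baseline sample is at least 20 percentage points greater", measured against baseline.
- The union of the two: "Treatment-emergent variant: A post-baseline variant or an enriched variant".

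The outputs then use four different terms.

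- **Listing by subject and time point:** "A listing by subject and time point of all treatment-emergent variants relative to the baseline amino acid sequences will be provided across all DAA targets". This includes enriched variants.
- **Count at virologic failure:** "The number and percentage of subjects with post-baseline variants at signature amino acid positions or emerged variants at non-signature amino acid positions". Signature positions are tied to *post-baseline*; non-signature positions are tied to *emerged*, which the SAP does not define.
- **First persistence count, at each post-treatment time point:** "The number and percentage of subjects with post-baseline variants at signature amino acid positions, listed by amino acid position and variant". Again *post-baseline*.
- **Second persistence summary, the proportion in whom a signature variant persists:** the denominator is subjects with the *emerged* variant at failure.
- **Count by number of targets:** "The number of subjects with resistance variants in 3 targets, 2 targets or 1 target will be provided". There is no post-baseline or enriched qualifier.

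Neither *enriched* nor *treatment-emergent* appears in any count summary.

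**The concern.** The n (%) tables are the trial's quantitative statement of which resistance variants the regimen selects and how long they last, out to Post-Treatment Week 260. A minority variant present before treatment that the drugs drive to dominance is selected resistance, and the SAP has a category for it. The signature-position counts nevertheless use the narrower category and give no reason.

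The error has one direction. Post-baseline variants are a subset of treatment-emergent variants, so a count restricted to the subset can equal or fall short of the full count but never exceed it. A reader who takes the table as the frequency of selected resistance at failure would be misled and would have to rebuild the count by hand from the listing.

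The undefined terms add a second problem. Two programmers could follow the same section and produce different persistence denominators and different target counts.

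**Working it through.** There is no plan figure to reproduce, so the check applies the SAP's definitions as rules.

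**Inputs (SAP 10.8).** Let *b* be baseline prevalence and *p* later prevalence, both in per cent.

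- Post-baseline: *b* < 2 and *p* ≥ 2.
- Enriched: present at both times and *p* − *b* ≥ 20. I read present as at least 2%, the detection level in the post-baseline definition.
- Treatment-emergent: either of the above.
- Entry to the signature-position counts (at failure, and the first persistence count): post-baseline only.

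**Results for illustrative prevalence pairs.** The pairs are assumptions; the documents give none.

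| *b* → *p* | Rise (points) | Post-baseline | Enriched | Treatment-emergent (listed) | In signature counts |
|---|---|---|---|---|---|
| 0 → 95 | 95 | yes | no | yes | yes |
| 1.9 → 95 | 93.1 | yes | no | yes | yes |
| 2 → 95 | 93 | no | yes | yes | **no** |
| 5 → 95 | 90 | no | yes | yes | **no** |
| 10 → 99 | 89 | no | yes | yes | **no** |
| 40 → 99 | 59 | no | yes | yes | **no** |
| 80 → 100 | 20 | no | yes | yes | **no** |
| 81 → 100 | 19 | no | no | no | no |
| 5 → 20 | 15 | no | no | no | no |

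The gap between listing and counts covers baseline prevalence from 2% up to 100 − 20 = 80%, the highest level from which a 20-point rise is possible.

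**Scale.** The number of subjects affected needs the share of failures that carry an enriched signature variant, and the documents do not give it. What can be shown is how much one omitted subject matters. Assume 2% to 4% of the 1650 subjects fail virologically. The Phase 3 figures in Protocol 3.0 run from zero (Study M13-389) to 7.8% (the ribavirin-free genotype 1a arm of Study M14-002, a regimen not assigned to genotype 1a subjects here).

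- 1650 × 0.02 = 33 failures, and 1650 × 0.04 = 66.
- One subject is then 1/66 = 1.5 to 1/33 = 3.0 percentage points of all failures.

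The planned table is grouped by subtype and limited to subjects with resistance data, so its denominators are smaller and each omission moves a percentage by more.

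**Persistence.** The imputation in SAP 10.8, also stated in SAP 6.3, works on whether a variant is detectable. Take an enriched variant that goes 5% → 95% → 5%. At the last time point it is still above 2%, so it is detectable and would be classed as persisting, although 5 − 5 = 0 points remain above baseline. Adding enriched variants to the persistence tables without a further rule would therefore overstate duration.

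**The case against.** The strongest defence is that counting newly appearing variants separately from pre-existing ones is a legitimate descriptive choice, and that Protocol 8.1.3 already defines a post-baseline variant as one not seen at baseline. That has some weight, but the protocol uses the term for by-subject listings under population sequencing. The n (%) counts of post-baseline variants are the SAP's own, and the SAP gives no reason for adding *enriched* and then leaving it out of them.

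Four stronger readings are tempting, and the documents do not support them.

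- **That enriched variants go unreported.** They appear in the treatment-emergent listing, and baseline variants at signature positions are listed too. What is missing is their place in the counts.
- **That the whole table at failure is limited to post-baseline variants.** The restriction applies to signature positions. Non-signature positions use *emerged*, which might include enriched variants.
- **That affected subjects drop out of every persistence result, or into a lower row of the target count.** The second persistence summary says *emerged* and the target count says *resistance variants*. Exclusion there is possible but not stated.
- **That a number of omitted subjects can be given.** Any such number rests on an enrichment frequency that the documents do not contain.

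Two limits on the remedy are also fair. A trivial change such as 1.9% to 2.0% would still be counted, because *treatment-emergent* includes every post-baseline variant. And the persistence tables need a new rule as well as a change of term.

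**Conclusion.** The point holds for two outputs: the signature-position count at virologic failure and the first persistence count at each post-treatment time point. Both omit enriched signature variants, which the SAP itself classes as treatment-emergent. The bias can only be towards understating resistance selected by the regimen, and its size cannot be computed from the documents. For the second persistence summary and the count by number of targets, the finding is ambiguity from undefined terms.

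The conclusion rests on a literal reading of the SAP's definitions, with present at baseline taken as 2% or more. That assumption does not affect the exclusion, because the post-baseline definition fixes its own cut-off at below 2%. The tables are descriptive, concern only subjects with virologic failure, and do not bear on the primary analysis. The change is worth making because it is cheap and the direction of the error is known.

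**What to change.** In SAP 10.8:

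1. In the count at virologic failure and the first persistence count, replace *post-baseline variants* at signature positions with *treatment-emergent variants (post-baseline or enriched)*. Show post-baseline and enriched as separate sub-rows, so that the count as now specified stays visible.
2. Define *emerged* as treatment-emergent, and base the count of subjects with variants in 3, 2 or 1 targets on the same definition.
3. For enriched variants in both persistence summaries, define persistence as still being at least 20 percentage points above baseline. Use that criterion in place of detectability in the imputation, and make the matching change in SAP 6.3. A return to the baseline level is then not counted as persistence.

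The cost is SAP wording, some extra table rows and one added persistence rule to program. No new samples or assays are needed: NGS prevalences are required by the existing definitions, and the enriched flag must already be derived for the listing.

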6.3 Missing Data Imputation

No data will be imputed for any efficacy or safety analyses except for the PRO questionnaires, for analyses of the HCV RNA endpoints, and for analysis of the persistence of resistance. If a respondent answers at least 50% of the items in a multi-item scale of the SF-36v2, the missing items will be imputed with the average score of the answered items in the same scale. In cases where the respondent did not answer at least 50% of the items, the score for that domain will be considered missing. Similarly, the missing items of the FACIT-F questionnaire will be imputed with the average score of the answered items in the same scale as long as more than 50% (≥ 7 out of 13) of the items in the scale are answered. The SF-36v2 Mental and Physical Component Summary measures will not be computed if any domain is missing.

HCV RNA values will be selected for an SVR analysis based on visit windows as defined in Section 6.2. When there is no HCV RNA value in a visit window based on defined visit windows, the closest values before and after the window, regardless of the value chosen for the subsequent and preceding window, will be used for the flanking imputation described below.

If a subject has a missing HCV RNA value at a post-Day 1 visit but with undetectable or unquantifiable HCV RNA levels at both the preceding value and succeeding value, the HCV RNA level will be considered undetectable or unquantifiable, respectively, at this visit for this subject. In addition, if a subject has an unquantifiable HCV RNA level at the preceding value and an undetectable HCV RNA level at the succeeding value, or vice versa, the HCV RNA level will be imputed as unquantifiable at this visit for this subject. For SVR analyses, if there is no value in the appropriate window after flanking imputation but there is an HCV RNA value after the window, then it will be imputed into the SVR window. Subsequent to this flanking and backward imputation, if a subject is missing a value for the visit window associated with the analysis, the subject will be imputed as a visit failure (i.e., not undetectable or unquantifiable).

If a subject starts another treatment for HCV, then all HCV RNA and PRO assessment values for this subject measured on or after the start date of the new HCV treatment will be excluded from analyses. The subject will be considered a failure for summaries of viral response at all time points after the start of the new HCV treatment.

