HCV RNA < LLOQ Analyses for SVR

If a subject is missing an HCV RNA value for the visit window associated with the analysis of SVR after performing the imputations described above, then this value will be imputed with an HCV RNA value from a local laboratory if present; otherwise, the HCV RNA value for this visit will be missing. Subjects with missing HCV RNA data in the analysis window, after imputations, will be imputed as a failure.

HCV RNA Analyses for Relapse and Virologic Failure

If HCV RNA values from the central laboratory are missing but a local laboratory value is present in the appropriate time period, then the local laboratory value will be used to assess post-treatment relapse and on-treatment virologic failure.

Finally, missing sequence data will be imputed as follows in the analysis of the persistence of resistance from the sequences from PT Week 52 through PT Week 260 (5 years). If a signature variant is not detectable by population, clonal or deep sequencing at PT Week 24 (or later), the variant is imputed as not detectable at the PT Week 52 (or timepoints after the sequence with the variant not detectable) and time points thereafter if a sample from Post-Treatment Week 52 or later is not sequenced. If a signature variant is detectable by population, clonal, or deep sequencing at Post-Treatment Week 52 or later, then the variant is imputed as being detectable at earlier time points if the sample at the earlier time point is not sequenced.

7.0 Demographics, Baseline Characteristics, Medical History, and Previous/Concomitant Medications

Demographics, baseline characteristics, medical history, and previous/concomitant medications will be summarized overall and by presence of cirrhosis and genotype 1 subtype on the safety population.

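### SAP 10.8 gives a persistence denominator that conflicts with its own imputation rule, and carries forward fewer variant losses than SAP 6.3

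*SAP*

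**What the plan says.** SAP 10.8 plans to report, for each variant and target, how many subjects still carry the variant at PT Weeks 24 and 52 and at time points up to PT Week 260. Four statements govern that percentage.

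- **Denominator (10.8).** It "will be calculated out of all subjects with that variant at VF who have sequencing at that time point". The sentence just before it words the total differently, referring to subjects with the emerged variant at failure and at that time point.
- **Stop rule (10.8).** If no resistance-associated variant is detected in a target at failure or in a post-treatment sample, "then that target will not be sequenced in subsequent samples from that subject".
- **Imputation (10.8).** Straight after the denominator, the section says imputation will be used from PT Week 52 to PT Week 260. For a variant not detectable at PT Week 24, "the variant is imputed as not detectable at the Post-Treatment Week 52 and time points thereafter", even without a sequenced sample. For a variant found at PT Week 52 or any subsequent visit, the rule reads: "then the variant is imputed as being detectable at earlier time points even if the sample at the earlier time point is not sequenced".
- **Imputation (6.3).** Imputation is allowed for the PRO questionnaires, "for analyses of the HCV RNA endpoints, and for analysis of the persistence of resistance". The forward rule has a wider trigger than in 10.8: "If a signature variant is not detectable by population, clonal or deep sequencing at PT Week 24 (or later"). The negative result then applies to time points after the sequence that showed the loss.

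**The concern.** The stop rule makes sequencing at a late visit depend on the outcome being measured. A subject whose target has cleared is not sequenced again; a subject who still carries a variant is. A denominator limited to sequenced subjects therefore loses people because they cleared the variant, which pushes late persistence upward. The imputation rule is the natural remedy, but the denominator sentence does not admit imputed results, and the two sections disagree on which losses are carried forward. Two programmers could follow the SAP and report different percentages.

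Persistence through PT Week 260 is a planned output (Protocol synopsis, Resistance; Protocol 8.1.3; SAP 10.8). The groups will be small. The sample size section assumes 4% of subjects miss SVR12, which for 1650 subjects is 0.04 × 1650 = 66. Only some of those are virologic failures, and they are then split by target and variant. A few omitted subjects can move a percentage a long way.

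**Working it through.** The documents state no persistence figure, so there is nothing to reproduce. The check has two parts.

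**1. How each imputed result enters the percentage.**

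- An imputed negative cannot change the numerator. It can act only by adding a subject to the denominator, and the literal denominator requires sequencing. Read that way, the forward imputation has no effect.
- An imputed positive can enter the numerator for a subject not sequenced at that visit, who is outside the literal denominator. For example, suppose three subjects are sequenced at PT Week 52 and all carry the variant. A fourth is not sequenced then but carries it at PT Week 104. The count becomes 4/3.
- The part of the stop rule triggered at failure does no harm here, because a subject without the variant at failure is not in the denominator anyway. The part triggered by a later negative sample matters.

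**2. What the choice of rule does to the result.**

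Assumptions (none from the documents): a fraction q of remaining carriers loses the variant in each interval; follow-up is complete; there is one variant per target and no re-emergence. Visits k = 1 to 6 are PT Weeks 24, 52, 104, 156, 208 and 260. True persistence is S(k) = (1 − q)^k. Subjects still sequenced at visit k are those positive at the visit before, S(k − 1).

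- Sequenced subjects only: S(k) / S(k − 1) = 1 − q at every visit.
- 10.8 carry-forward, imputed subjects counted: S(k) / [S(k − 1) + q] for k ≥ 2, because only the PT Week 24 losses (q) are added back.
- 6.3 carry-forward, imputed subjects counted: S(k), the true value.

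With q = 20%:

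- PT Week 52: 0.64/0.80 = 80.0%; 0.64/(0.80 + 0.20) = 64.0%; 64.0%.
- PT Week 104: 0.512/0.64 = 80.0%; 0.512/(0.64 + 0.20) = 61.0%; 51.2%.
- PT Week 260: 0.2621/0.3277 = 80.0%; 0.2621/(0.3277 + 0.20) = 49.7%; 26.2%.

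PT Week 260 across assumed loss rates (excess over the 6.3 value, from unrounded figures, in brackets):

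| q | Sequenced only | 10.8 carry-forward | 6.3 carry-forward |
|---|---|---|---|
| 10% | 90.0% (+36.9) | 77.0% (+23.8) | 53.1% |
| 20% | 80.0% (+53.8) | 49.7% (+23.5) | 26.2% |
| 30% | 70.0% (+58.2) | 25.1% (+13.4) | 11.8% |
| 50% | 50.0% (+48.4) | 2.9% (+1.4) | 1.6% |

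In assumed counts: 40 carriers at failure, with 10, 10 and 5 losing the variant at PT Weeks 24, 52 and 104 and none after.

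| Visit | Sequenced only | 10.8 carry-forward | 6.3 carry-forward |
|---|---|---|---|
| PT Week 52 | 20/30 = 66.7% | 20/40 = 50.0% | 20/40 = 50.0% |
| PT Week 104 | 15/20 = 75.0% | 15/30 = 50.0% | 15/40 = 37.5% |
| PT Week 260 | 15/15 = 100% | 15/25 = 60.0% | 15/40 = 37.5% |

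Under the first two countings, reported persistence rises between PT Weeks 52 and 260 although no variant has re-emerged. The rise comes entirely from the shrinking denominator.

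**The case against.** The strongest reply is that the SAP already deals with this. The sentence after the denominator invokes imputation for PT Week 52 to PT Week 260, 6.3 names persistence among the imputed analyses, and the forward rule is aimed at samples not sequenced after a loss. Since an imputed negative can affect this percentage only through the denominator, the authors very likely meant imputed subjects to be counted. That is a fair reading of intent. With the 6.3 rule it removes the bias in the illustration.

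A reader might therefore go too far and infer that the plan makes late persistence biased upward whatever is done. The documents do not support that. A loss seen at PT Week 24, for instance, is covered by the forward rule in both sections once imputed subjects are counted. The stop rule also works per target: a subject who loses one variant but keeps another in the same target remains sequenced and counts as a negative, so the excess would be smaller than the sequenced-only column shows.

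It is also true that persistence is not among the objectives or the primary and secondary variables, that no test or power depends on it, and that listings by subject and time point are planned.

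What the reply does not remove is the literal denominator, the possible numerator-only positives, and the narrower 10.8 trigger. Likely intent does not settle which of two conflicting sections a programmer follows.

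**Conclusion.** The point stands as a conflict between stated rules. The SAP 10.8 denominator excludes the results that its own imputation creates, and its forward rule covers only losses at PT Week 24 where 6.3 covers later ones too. If 10.8 alone is followed, with imputed subjects counted, subjects who first lose the variant at PT Week 52 or later leave the denominator and late persistence is overstated. In the illustration the excess at PT Week 260 is 1.4 to 23.8 points for assumed loss rates of 10% to 50% per interval. If only sequenced subjects are counted, it is 36.9 to 58.2 points over the same assumed rates.

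If 6.3 is applied and imputed subjects are counted, this bias disappears. One possible exception is a target stopped on a post-treatment sample before PT Week 24, which neither forward rule names.

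The direction follows from the stop rule. The sizes rest on assumed loss rates, complete follow-up and one variant per target. The effect is confined to a descriptive resistance summary; the primary analysis is untouched.

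**What to change.** - In SAP 10.8, define the denominator as all subjects with the variant at virologic failure who have a sequenced or imputed result at that time point. Use the same definition in the sentence before it, and take the numerator from that set.
- Align the 10.8 forward rule with 6.3, so that any loss first seen at PT Week 24 or later is carried to later unsequenced time points.
- In both sections, extend the rule to targets whose sequencing stopped on a post-treatment sample before PT Week 24.
- In the table, show observed and imputed counts separately at each time point.

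The cost is a few sentences in 10.8, a clause in 6.3 and extra table columns. No new samples, sequencing or data collection are needed.
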